17.2.3. SENSITIVITY ANALYSIS OF PRIMARY AND KEY SECONDARY EFFICACY VARIABLES

17.2.3.1. Analysis Using Derived Stratification Factors

In order to assess any potential impact to the efficacy result from mis-stratification, the stratification factors of disease characters and statin intensity will be derived in cases there is a known stratification error. The primary endpoint will be re-analyzed using the same method as described in [section 17.1.2](#) using derived stratification factors.

17.2.3.2. Adjunctive Lipid-modifying Therapy (LMT) Analysis

To explore the potential impact from adjunctive lipid-modifying therapy use during the study, a sensitivity analysis will be performed for primary and key secondary endpoints using data prior to the change of the post-baseline LMT only, i.e., lab test date <=change date of LMT. There will be no imputation for missing data.

Statistical Analysis Plan

17.2.3.3. On-treatment Analysis

To explore the impact to efficacy from patient discontinue study medication, an on-treatment analysis will also be conducted for primary and key secondary endpoints using data collected from the on-treatment period, i.e. lab test date \leq of last dose of double-blind IMP+7 days. On-treatment analysis will be based on FAS. There will be no imputation for missing data.

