9.2. Administration of Investigational Medicinal Product

Patients will be instructed to ingest, placebo starting at Visit S2 for the duration the placebo run-in period and the IMP starting at Visit T1 for the duration of treatment period orally once daily (once every 24 hours) at approximately the same time each day with water. IMP may be taken with or without food. On clinic visit days, patients will be instructed to delay ingestion of IMP until all study procedures have been completed. If a patient arrives at clinic on Visits T4 or T5 or T7 without having fasted or having taken IMP before arriving at the clinic, reschedule the visit (the next day or as soon as possible) so that the fasting and dosing requirements have been met. Patients will be instructed to return all packaging and unused IMP at each clinic visit.

If the patient forgets to take IMP at the usual time on nonclinic visit days, it may be taken up to 12 hours later the same day. After that time, the patient should not take IMP that day and should resume ingestion of IMP the following day. If a patient fails to take IMP, details describing the reasons for nondosing should be documented in the patient's medical records and eCRF. Extra IMP (7 extra days per bottle) is provided and can be used, if needed, prior to the next visit or to replace a dose of IMP that cannot be used because it is lost or damaged.

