10.3. Subject Withdrawal Criteria

10.3.1. Early Withdrawal from the Study

Patients must remain in the study until the last scheduled visit at Week 52 (Visit T7) to be considered as having completed participation in the study.

Patients who withdraw from IMP prior to Week 52 (Visit T7) for any reason will be asked to continue to be followed for safety assessments, including basic fasting lipids, at clinic visit following the protocol-specified visit schedule (see [Appendix 1](#)).

Patients who temporarily withdraw from IMP prior to Week 52 (Visit T7) for any reason may restart IMP providing that 1) the patient and the investigator are in agreement regarding this course of action, 2) the patient has been off of IMP for 4 weeks or less; and 3) IMP can be started as soon as possible. For cases where the patient has been off of IMP for more than 4 weeks, the investigator must contact the medical monitor for approval prior to restarting IMP.

Patients who refuse to continue to return to the clinic for safety assessments will be asked to participate in phone calls from the site at protocol-specified visits (see [Appendix 1](#)), or at a minimum at 52 weeks, to collect information on AEs, concomitant medications, and current health status. The patient must provide consent to be contacted by phone by site personnel for the purposes of assessing current AEs and current health status.

The patient's decision to participate in the clinical study is voluntary. Patients may refuse to continue in the study and/or withdraw from participation in this study at any time, for any reason, specified or unspecified, and without penalty or loss of benefits to which the patient is otherwise entitled.

It is the right and duty of the Investigator to interrupt the treatment of any patient whose health or well-being may be threatened by continuation in this study. Such patients should be withdrawn from the study and should not be continued under a modified regimen.

Patients who are withdrawn from the study may not re-enter. The reasons for withdrawal from this study may include:

- Patient's withdrawal of consent
- Failure to comply with the protocol
- Lost to follow-up
- Illness, condition, or procedural complication (including AEs) affecting the patient's ability to participate or requiring prohibited medication
- The Sponsor or Investigator terminates the study

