11.1.6.3.1. Monitoring and Management of Elevated Liver Function Tests

If at any time after randomization a patient experiences a new ALT and/or AST $>3 \times$ ULN, the patient will undergo repeat confirmatory liver function test (LFT) assessment as soon as is reasonably possible, preferably within 3 to 7 days of the laboratory result becoming available.

Repeat LFT assessment will include: 1) measurement of ALT, AST, alkaline phosphatase, total and direct bilirubin, prothrombin time (PT)/international normalized ratio (INR), eosinophil count, CK, antihepatitis A virus (total), HBsAg (confirmation of screening measurement), HCV (confirmation of screening measurement), and anti-cytomegalovirus/immunoglobulin M; 2) history of concomitant medication use; 3) history of exposure to environmental chemical agents, including ethanol; and 4) query for related symptoms. Additionally, further testing such as liver ultrasound or magnetic resonance imaging (MRI) scanning may be warranted to rule out additional pathology depending on clinical presentation and should be discussed with the Sponsor personnel or the authorized Medical Monitor.

- If repeat LFT assessment confirms ALT and/or AST $>3 \times$ ULN, consideration should be given to withdrawing the patient and administering no further doses of study drug. At the investigator's discretion, study drug may be interrupted and the patient rechallenged with study drug after LFTs have returned to baseline levels.
- If repeat LFT assessment confirms ALT and/or AST $>5 \times$ ULN, patient should be withdrawn from IMP treatment, but will be asked to continue to be followed for safety using the protocol-specified visit schedule (see [Appendix 1](#)) or more frequently if deemed by the investigator.
- If repeat LFT assessment confirms ALT and/or AST $>3 \times$ ULN in addition to any of the following, the patient should be given no further IMP treatment, but will be asked

to continue to be followed for safety using the protocol-specified visit schedule (see [Appendix 1](#)) or more frequently if deemed by the investigator:

- TB $>2 \times$ ULN

Note: In the case of patients with Gilbert's disease, TB will be fractionated and the determination of $2 \times$ ULN will be based upon direct (conjugated) bilirubin.

- INR $>1.5 \times$ ULN (unless the patient is on stable dose of anticoagulation medication)

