16.1. DERIVATIONS

Compliance with placebo-run in (as an overall group) and double-blind study medication by treatment group, based on the drug accountability data, will be calculated as the number of tablets taken (total dispensed – total returned) divided by the number of days on treatment within each of the 2 periods.

During the run-in period, the compliance will be summarized as a single overall group and during the double-blind period, compliance will be summarized by treatment group (bempedoic acid and placebo).

Compliance will not be computed by visit.

A 35-day supply of single-blind placebo drug will be dispensed one time at Week -4 (Visit S2) for the 4-week placebo run-in period of the study. Double-blind IMP will be dispensed in 100 day supply increments to patients by appropriate clinical site personnel. Patients will receive one 100-day supply bottle at Week 0 (Visit T1), Week 12 (Visit T4), and two 100-day supply bottles at Week 24 (Visit T5).

The treatment is taken once daily and it is assumed that the patient takes medication on the visit day at which their medication is initially dispensed to the day of their last medication return date. For example, if the initial dispense date is Day 1 and the last return date is Day 84, then the patient should have taken the first tablet at Day 1, once a day on Days 2 to 83 and 1 tablet on Day 84; hence, the total number of prescribed tablets would be 84.

For subjects who did not return any bottle during the run-in or double-blind period, their compliance will be set to missing.

Treatment exposure will be calculated in weeks as (date of last dose of study medication – first date of first dose of study medication +1)/7. Descriptive statistics will be presented for exposure as well as categorization into time periods. (e.g., <12weeks, 12-<24 weeks, 24-<48 weeks and >=48 weeks, etc.).

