17.1.3. MISSING DATA METHODS FOR PRIMARY EFFICACY VARIABLE

For the primary endpoint of percent change from baseline to Week 12 in LDL-C values, a pattern mixture model (PMM) will be used to specify different imputation strategies depending on whether the patient is still on study treatment. Patients with missing lipid data at Week 12 who are no longer taking study treatment (defined by date of last dose of study medication is < Week 12 visit date -7) can be assumed to no longer be benefitting from study medication, and their missing value(s) can be assumed to be similar to those in placebo group who remained on study and have data. To account for uncertainty, missing values will be imputed using multiple imputation via a regression based model including stratification and baseline data from placebo subjects only. In this imputation model, treatment group will not be included as a factor.

Patients with missing lipid data at Week 12 who are still taking study treatment (date of last dose of study medication is ≥ Week 12 visit date -7) can be assumed to continue to benefit from study medication, and their missing value(s) can be assumed to be similar to those who remain on study treatment and have data and as a result, lipid values will be imputed based on the observed values in their randomized treatment group at Week 12. To account for uncertainty, missing values will be imputed using multiple imputation via a regression based model including treatment, stratification and baseline data.

Imputed datasets will be analyzed using an ANCOVA model with treatment, CV risk, baseline statin intensity as a factors and baseline LDL-C as a covariate. Approximately 200 imputed datasets will be created, with results from the analysis of each imputed dataset combined using Rubin’s method. The least squares mean (LSM) and standard error (SE) will be provided for both treatment groups, along with the placebo-corrected LSM, its 95% confidence interval (CI) and associated p-value. To account for possibility of unequal variances between the groups, the ANCOVA model will be implemented within mixed model framework where <repeated/group=> option will be used to allow separate estimation of residual variance between the groups.

Further information on the multiple imputation method is presented in [Appendix 4](#).

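### Judging on-treatment status by one last-dose date counts patients in an IMP interruption at Week 12 or 24 as on treatment if they later restart (low priority)

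*SAP*

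**What the plan says.** **Protocol.** Section 10.3.1 treats interruption as an expected state: "Patients who temporarily withdraw from IMP prior to Week 52 (Visit T7) for any reason may restart IMP". The conditions are agreement between patient and investigator, a prompt restart and no more than 4 weeks off IMP. A longer gap needs medical monitor approval, and no upper limit is stated. For confirmed liver enzyme elevations, section 11.1.6.3.1 adds that, at the investigator's discretion, "study drug may be interrupted and the patient rechallenged with study drug after LFTs have returned to baseline levels". Section 11.1.6.3.4 has IMP held for symptomatic, confirmed CK elevation, with resumption possible if another explanation is suspected.

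**SAP.** Three rules use one last-dose date and none mentions a gap in dosing:

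- 17.2.3.3 (on-treatment analysis) keeps values dated on or before the date "of last dose of double-blind IMP+7 days. On-treatment analysis will be based on FAS".
- 17.1.3 (imputation) calls a patient with a missing Week 12 value off treatment when "defined by date of last dose of study medication is < Week 12 visit date -7". Otherwise the patient "can be assumed to continue to benefit from study medication" and the value is imputed from the randomized arm. Appendix 4 applies the same approach at Week 24, and 17.2.1 carries it to the key secondary endpoints.
- 16.1 (exposure): "Treatment exposure will be calculated in weeks as" last dose minus first dose plus one day, divided by seven.

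**The concern.** For a patient who restarts, the last-dose date falls after the visit in question. Status at Week 12 is then decided by what happens after Week 12. Two patients with the same dosing history up to Day 85 are classified differently because one of them resumes later.

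This conflicts with the reasoning in SAP 17.1.3, where own-arm imputation is justified because the patient is still taking the drug. An interrupted patient passes the date test but does not meet that assumption. Two results could be affected. The on-treatment analysis would contain off-drug values. Some missing values in the primary and key secondary analyses would be imputed from the wrong reference group, in the drug's favour.

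**Working it through.** **1. The plan's own figure.** SAP 7.1 gives 500 and 250 patients, a 15-point difference, SD 15 and two-sided alpha 0.05.
- SE of the difference = 15 × √(1/500 + 1/250) = 1.16 points.
- Noncentrality = 15 / 1.16 = 12.9 on 748 df, so power is 1.000. The stated figure of more than 95% is reproduced.

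**2. The date rules applied to example histories.** Assume the final dose is on Day 364. Target days (85 and 168) are from SAP 6.4.

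| History | Visit | SAP on-treatment rule | SAP imputation rule | Most recent dose before visit |
|---|---|---|---|---|
| Off IMP Days 70–97 (28 days), restart Day 98 | Day 85 | 85 ≤ 371: kept | 364 < 78 is false: on | Day 69; 85 > 76 and 69 < 78: off |
| Last dose Day 69, never restarts | Day 85 | 85 > 76: dropped | 69 < 78: off | Day 69: off |
| Off IMP Days 154–181 (28 days), restart Day 182 | Day 168 | 168 ≤ 371: kept | 364 < 161 is false: on | Day 153; 168 > 160 and 153 < 161: off |

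The first two patients are in the same state on Day 85 but are classed differently.

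**3. Whether the 7-day allowance excuses this.** Protocol 4.2.3 gives half-lives of up to 27 h (parent) and 33 h (metabolite). Seven days is 168/27 = 6.2 and 168/33 = 5.1 half-lives. The allowance already covers washout of the drug, so a longer gap cannot be treated as time on drug.

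**4. How a hold can reach the visit.** A 28-day gap starting on day s covers Day 85 if s + 27 ≥ 85, and puts the last dose more than 7 days earlier if s − 1 < 78. So s lies between Day 58 and Day 78. Protocol Appendix 1 has no scheduled safety laboratory tests in that interval; Week 8 is a telephone visit. A hold from Day 29 results, with a repeat within 7 days and 28 days off, ends at about 29 + 7 + 28 = Day 64, plus the time taken to report results.

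**5. Dilution in the on-treatment analysis.** Let f be the share of the active arm misclassified at the visit. Assume their values are fully back to baseline and placebo is unaffected. Effect = 15 × (1 − f). The rates are assumed, because the documents give none.

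| f | Patients of 500 | Effect | Shift |
|---|---|---|---|
| 1% | 5 | 14.85 | 0.15 |
| 2% | 10 | 14.70 | 0.30 |
| 5% | 25 | 14.25 | 0.75 |
| 10% | 50 | 13.50 | 1.50 |

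Power stays at 1.000 throughout.

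**6. Shift in the primary analysis.** Let g be the share of the active arm both interrupted and missing. Shift ≤ 15 × g. For an assumed 0.2% to 2% (1 to 10 patients) that is 0.03 to 0.30 points in the drug's favour, at most 0.30/1.16 = 0.26 SE. It is an upper bound: in Appendix 4 the own-arm model for bempedoic acid draws on cohorts 6 and 8, and cohort 8 is patients off treatment with observed values.

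**7. Exposure.** A 4-week gap gives 52 weeks recorded against 48 on drug (4/48 = 8.3% over). An 8-week gap gives 52 against 44 (8/44 = 18.2% over) and moves the patient from the 24 to under 48 week category to the 48-week-or-more category.

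**The case against.** The strongest reply is that few patients can be affected and that the primary analysis is largely protected. Most of it stands.

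- **Observed values.** The primary analysis uses an observed Week 12 value whatever the dosing. The analysis windows in SAP 6.4 are wide (Days 72–127 for Week 12, Days 128–211 for Week 24), and unscheduled samples can fill them. The first patient in the table would have nothing imputed if a lipid sample were drawn by Day 127.
- **Laboratory-driven holds.** As step 4 shows, a hold of 4 weeks or less that follows scheduled tests would usually end before the visit. Misclassification needs an unscheduled finding, another reason for stopping, or a longer gap with approval. The liver interruption is discretionary and the CK hold covers symptomatic cases only.
- **Purpose.** SAP 17.2.3.3 says it explores the effect of discontinuing medication, and a last-dose cutoff suits permanent discontinuation. But the section also confines the data to the on-treatment period, and an interrupted patient at the visit is outside it on any ordinary meaning. The bias there is at least conservative.
- **Exposure.** Last minus first dose is a measure of treatment duration, and 16.1 also reports compliance. A 28-day gap in 364 days would lower that to 336/364 = 92%. This is largely a matter of labelling. Compliance is not computed by visit, however, and feeds no on-treatment rule.

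A reader might infer that interruptions inflate the primary result in general, or that interrupted patients are imputed as if taking the drug. The documents support neither. The first needs the value to be missing as well, and the second overlooks cohort 8.

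**Conclusion.** The point holds as a misclassification rule of small consequence. A patient more than 7 days off IMP at the visit who later restarts is counted as on treatment, against the SAP's own rationale. The on-treatment estimate is diluted. The primary and key secondary estimates move slightly in the drug's favour, and only for patients whose value is still missing after windowing.

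The most exposed key secondary endpoints are apoB and hs-CRP. The note to Protocol Appendix 1 leaves them out of assessments after IMP withdrawal. If sites apply that note to temporary withdrawals (the protocol does not say), these values would be missing because the patient is off drug, and would then be imputed from the patient's own arm inside the hierarchical testing sequence. The documents give no planning effect for either, so no size can be put on it.

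For LDL-C the shift is at most about 0.15 points per 1% of active-arm patients affected. This assumes the planned 15-point effect and full return to baseline. It also takes the last-dose date to be the final one. The SAP does not use the word final, but that is the plain reading, and Protocol 10.3.2 has a last-dose date recorded at withdrawal. Power and the primary conclusion are not at risk. Priority: low.

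**What to change.** In SAP 17.1.3, 17.2.3.3 and Appendix 4, call a patient on treatment only if the most recent dose on or before the sample date, or the target visit day if there is no sample, is within 7 days. Fall back to the present last-dose rule where interruption dates are not recorded. Optionally, label the 16.1 measure as treatment duration and also show exposure net of recorded interruptions. The clinical rules for interrupting and restarting IMP are not at issue.

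The cost is SAP wording and programming, using data the trial already collects: nondosing entries, the adverse event field for action taken with study drug (SAP 18.1.4) and tablet counts (Protocol 8.3). The downside is dependence on how completely interruption dates are recorded. Protocol 9.2 requires that "details describing the reasons for nondosing should be documented", which covers reasons but does not explicitly ask for start and stop dates. The times of the last two doses are recorded only with PK samples at Weeks 24 and 52, so they do not help at Week 12.

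The SAP addendum reports that the planned analyses are complete and the study unblinded. For this trial the change would therefore be a supplementary rerun, labelled as such.

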17.2.3.4. Observed Data Analysis

The observed case data with no imputation for missing data will be used in sensitivity analyses for primary and key secondary endpoints to explore any difference between a observed analysis vs. missing data imputation using PMM method.

17.2.4. **SUBGROUP ANALYSIS OF PRIMARY EFFICACY VARIABLE**

The primary endpoint for LDL-C will be analysed within subgroups below using the same analysis method previously described. The treatment and subgroup interaction will be examined by including the interaction term in the ANCOVA model for the overall population first. No imputation will be performed on missing data for subgroup analyses. In case the number of subjects within a subgroup is too small, e.g. less than 5% of the overall population, the analyses may not be performed or the subgroup levels may be combined. Forest plots for the primary efficacy variable will also be presented.

- CV risk category (HeFH (with or without ASCVD) vs. ASCVD only)
- Baseline statin intensity (Low or Moderate, vs. High)
- Baseline LDL category ($<130\text{mg/dL}$, $\geq 130\text{ mg/dL}$ and $< 160\text{ mg/dL}$, $\geq 160\text{mg/dL}$) (efficacy only)
- History of diabetes (yes vs.no)
- Age ($< 65\text{ yrs.}$ vs. $\geq 65\text{ yrs.}$ and $<75\text{ yrs}$ vs. $\geq 75\text{ yrs}$)
- Race (White vs. other)
- Gender (male vs. female)
- Region (North America vs. EU)
- BMI category (< 25 vs. $25 - < 30$ vs. $\geq 30\text{ kg/ m}^2$)

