4.2.4. Dose Selection

Doses of bempedoic acid ranging from 40 to 240 mg/day have been evaluated in the Phase 2 program. Based on data from the integrated analysis of safety and efficacy, observed values and percent change from baseline in the primary efficacy endpoint, LDL-C together with a positive safety profile, support the choice of the 180-mg dose for the Phase 3 studies. An integrated analysis of six Phase 2 studies resulted in placebo-adjusted least square (LS) means for percent change from baseline of approximately 32% with bempedoic acid 180 mg monotherapy, 50% with bempedoic acid 180 mg + ezetimibe 10 mg, and 22% for 180 mg on top of stable statin therapy. The 180-mg dose was noted to have an excellent safety profile. Overall, balancing efficacy and safety the 180-mg dose was chosen for the Phase 3 program.

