Atorvastatin 40-80 mg	Atorvastatin 10-20 mg	Simvastatin 10 mg
Rosuvastatin 20-40 mg	Rosuvastatin 5-10 mg	Pravastatin 10-20 mg
	Simvastatin 20 mg	Lovastatin 20 mg
	Pravastatin 40-80 mg	Fluvastatin 20-40 mg
	Lovastatin 40 mg	Pitavastatin 1 mg
	Fluvastatin XL 80 mg	
	Fluvastatin 40 mg BID	
	Pitavastatin 2-4 mg	

^a Simvastatin doses ≥ 40 mg/day are not allowed.

^b Low intensity statins also include those patients taking low-dose statins using an alternate regimen (ie, every other day, or for a specified number of times per week) and those unable to tolerate a statin at any dose.

Table 3: Randomization Strata

HeFH (with or without ASCVD)	ASCVD (without HeFH)
HeFH + Low Intensity Statins ^a	ASCVD + Low Intensity Statins ^a
HeFH + Moderate Intensity Statins	ASCVD + Moderate Intensity Statins
HeFH + High Intensity Statins	ASCVD + High Intensity Statins

ASCVD = Atherosclerotic cardiovascular diseases; HeFH = Heterozygous familial hypercholesterolemia.

^a Low intensity statins also include those patients taking low-dose statins using an alternate regimen (ie, every other day, or for a specified number of times per week) and those unable to tolerate a statin at any dose.

[figure not shown]
Approximately 750 eligible patients will be randomized 2:1 on Day 1 (Visit T1) to receive either bempedoic acid 180 mg (n = 500), or placebo (n = 250) once daily for 52 weeks. Randomized patients will return for clinic visits at Week 4 (Visit T2), Week 12 (Visit T4), Week 24 (Visit T5), and Week 52 (Visit T7). A phone visit will occur at Week 8 (Visit T3) and Week 36 (Visit T6).

Patients who withdraw from investigational medicinal product (IMP) treatment will be asked to continue to be followed for safety using the protocol-specified visit schedule. For details of study assessments, see the Schedule of Events in [Appendix 1](#).

An independent expert Data Monitoring Committee (DMC) will formally review accumulating unblinded safety and efficacy data from this and other ongoing studies of bempedoic acid. A blinded independent expert Clinical Events Committee (CEC) will adjudicate designated clinical endpoints, including all major adverse cardiac events (MACE) and non-MACE endpoints defined as: CV death (MACE), non-CV death (non-MACE), nonfatal myocardial infarction [MI] (MACE), nonfatal stroke (MACE), hospitalization for unstable angina (MACE), coronary revascularization (MACE), non-coronary arterial revascularization (non-MACE), and

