7. STATISTICAL CONSIDERATIONS

7.1. SAMPLE SIZE

The primary efficacy endpoint for this study is the percent change from baseline to Week 12 in LDL-C.

The sample size of 500 randomized patients in the bempedoic acid 180 mg group and 250 randomized patients in the placebo group is expected to provide more than 95% power to detect a difference of 15% in the percent change from baseline to Week 12 in LDL-C between the bempedoic acid treatment group and the placebo group. This calculation is based on a 2-sided t-test at the 5% level of significance ($\alpha = 0.05$) and a common standard deviation of 15%. The sample size of 500 randomized patients in the bempedoic acid 180 mg group and 250 randomized patients in the placebo group gives a total study sample size of 750.

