17.1.2. PRIMARY ANALYSIS OF PRIMARY EFFICACY VARIABLE

The null hypothesis, H_0 , will be that there is no difference between bempedoic acid 180 mg/day and placebo in mean percent change from baseline to Week 12 in LDL-C. The alternative hypothesis, H_1 , will be that bempedoic acid 180 mg/day is different from placebo:

$$H_0: \mu_p = \mu_b$$

$$H_1: \mu_p \neq \mu_b$$

where μ_p and μ_b denote the mean percent change from baseline to Week 12 in LDL-C on placebo and bempedoic acid 180 mg/day respectively.

The primary efficacy endpoint will be analyzed using analysis of covariance (ANCOVA), with treatment group and randomization stratification factors (CV risk and baseline statin intensity) as factors and baseline LDL-C as a covariate. In case the of number of subjects within a stratum is too small for a meaningful analysis, the strata may be combined to obtain larger cell size. The ANCOVA will be performed using the FAS, with patients included in their randomized treatment group regardless of the treatment they actually received. To account for the likelihood of unequal variances between the treatment groups, the ANCOVA model will be implemented within mixed model framework and the <repeated/group=> option will be used to allow estimating the residual variances separately between the groups. Assumptions for ANCOVA model will be assessed and if the assumptions are severely violated, a non-parametric rank based method will be performed.

In addition, descriptive statistics will be presented for LDL-C at each visit and for change/percent change from baseline by treatment group for overall population and for each stratification factor.

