18.1.1. ALL TEAEs

Incidence of TEAEs will be presented by System Organ Class (SOC) and Preferred Term (PT) and also broken down further by maximum severity and relationship to study medication. TEAEs will also be presented by PT in descending frequency. Adverse events by the subgroups in [Section 17.2.4](#) with the exception of baseline LDL subgroup will also be presented.

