Esperion completed the planned analysis as described in Study 1002-047 SAP for all data collected in the study. After unblinding, additional tables and figures were generated to address some issues of clinical interest.

The tables and figures may be presented in the manuscript, presented in the top line results press release, reported in the CSR, and included the communications with the regulatory agencies for the NDA/MAA submissions.

The listing of tables and figures for the post-hoc analyses is provided in the table below.

Table 17.2.4.1a	Efficacy Subgroup Analysis: Percent Change from Baseline to Week 12 in Low Density Lipoprotein Cholesterol (LDL-C) by Derived Baseline Statin Intensity / Full Analysis Set
Table 17.2.4.1b	Efficacy Subgroup Analysis: Percent Change from Baseline to Week 12 in Low Density Lipoprotein Cholesterol (LDL-C) by Baseline Lipid-modifying / Therapies (LMT) Medications Full Analysis Set
Table 17.2.2.6a	Key Secondary Efficacy Non-parametric Analysis: Wilcoxon Rank Sum Test on Percent Change from Baseline to Week 12 and 52 in High-Sensitivity C-reactive Protein (hsCRP) by Derived Baseline Statin Intensity / Full Analysis Set
Table 17.2.2.6b	Key Secondary Efficacy Non-parametric Analysis: Wilcoxon Rank Sum Test on Percent Change from Baseline to Week 12 and 52 in High-Sensitivity C-reactive Protein (hsCRP) by Baseline Lipid-modifying Therapies (LMT) Medications / Full Analysis Set
Table 17.2.2.6c	Key Secondary Efficacy Non-parametric Analysis: Wilcoxon Rank Sum Test on Percent Change from Baseline to Week 24 and 52 in High-Sensitivity C-reactive Protein (hsCRP) On-Treatment Analysis / Full Analysis Set
Table 17.3.1.1	Incidence of Positively Adjudicated Treatment-Emergent Composite Clinical Endpoints / Safety Analysis Set
Table 17.4.1.1	Post-Randomization Abnormal Liver Function Summary / Safety Analysis Set
Figure 19.1.1	Waterfall Plot of Percent Change from Baseline to Week 12 in Low Density Lipoprotein Cholesterol (LDL-C) / Full Analysis Set

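### The statin-intensity subgroup merges the low level (which includes no statin) with moderate, so a no-statin versus statin difference would be heavily diluted; reporting the three randomized levels is a cheap improvement

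*SAP*

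**What the plan says.** Protocol 6.1 (Tables 2 and 3) stratifies randomization by high, moderate and low statin intensity, crossed with two CV-risk groups. Footnote b to Table 2 places in the low level both patients on low-dose alternate regimens and "those unable to tolerate a statin at any dose". The SAP keeps three levels in its covariate list (7.2) and baseline table (11), and the primary ANCOVA (17.1.2) uses the randomization factors.

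Only SAP 17.2.4 changes the grouping. The subgroup model, interaction term and forest plot use "Baseline statin intensity (Low or Moderate, vs. High". The same section already allows a subgroup below about 5% of the population to be skipped or combined, and it keeps three levels for baseline LDL-C and BMI.

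Two other places matter. SAP 17.1.2 plans descriptive LDL-C statistics by arm "for overall population and for each stratification factor". SAP 18.1.1 carries the 17.2.4 groupings into the adverse-event tables, "with the exception of baseline LDL subgroup will also be presented".

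Protocol 4.2.4 gives the Phase 2 placebo-adjusted effects: about 32% as monotherapy and "22% for 180 mg on top of stable statin therapy".

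**The concern.** If the effect varies with statin background, the documents point to one place for it: between patients on no statin and patients on a statin. The merged group contains that boundary. The single planned interaction test for statin intensity compares high with everything else, a contrast for which the documents report no difference in effect. Sparse data do not explain the merger, because the small-subgroup rule would handle that once the counts are known.

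At stake is a pre-specified answer on whether the effect differs in patients on little or no statin. The adverse-event subgroup tables inherit the grouping, so patients without any statin exposure are pooled there with statin users.

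**Working it through.** **The plan's own figure.** SAP 7.1 sizes the trial "to detect a difference of 15% in the percent change from baseline to Week 12 in LDL-C" with 500 and 250 patients and SD 15. "This calculation is based on a 2-sided t-test at the 5% level of significance". SE = 15 × √(1/500 + 1/250) = 1.162, and 15/1.162 = 12.91, so power exceeds 99.9%. This agrees with the stated figure of more than 95%.

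**Inputs from the documents.** N = 750 at 2:1, SD 15, two-sided 5% level, effects of 32 points without a statin and 22 points on a statin.

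**Assumptions, not in the documents.** The share in each level, the share of the low level on no statin, the same 22-point effect at any statin dose, no missing data, and SD 20 as a sensitivity value.

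**Formulas.**
- Variance of the treatment effect in a subgroup of size n: SD² × [1/(2n/3) + 1/(n/3)] = 4.5 × SD²/n, which is 1012.5/n at SD 15.
- Two levels: z test of merged minus high.
- Three levels: noncentral chi-square with 2 df, noncentrality = Σ (effect − weighted mean)² / variance.

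**Base case.** Shares 50/40/10% give 375 high, 300 moderate and 75 low; all low-level patients are on no statin.
- Merged effect = (300 × 22 + 75 × 32)/375 = 24, against 22 in high: a 2-point difference.
- SE = √(1012.5/375 + 1012.5/375) = 2.32; power 14%.
- Three levels: weighted mean 23; noncentrality = 81/13.5 + 1/3.375 + 1/2.7 = 6.67; power 63%.
- Low level alone: SE = √(1012.5/75) = 3.67; 95% CI half-width 7.2 points.

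**Varying the assumptions** (the low-level effect is 22 + 10 × the no-statin share):

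| High/mod/low | Low level on no statin | SD | Merged − high | Two-level power | Three-level power |
|---|---|---|---|---|---|
| 50/40/10 | all | 15 | 2.0 | 14% | 63% |
| 50/40/10 | half | 15 | 1.0 | 7% | 19% |
| 50/40/10 | quarter | 15 | 0.5 | 6% | 8% |
| 50/40/10 | all | 20 | 2.0 | 10% | 39% |
| 50/40/10 | half | 20 | 1.0 | 6% | 13% |
| 50/30/20 | all | 15 | 4.0 | 41% | 88% |
| 50/30/20 | half | 15 | 2.0 | 14% | 32% |

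**Wider range.** With the high level at 40–60%, the low level at 5–20% and SD 15, the two-level contrast keeps 8–50% of the difference. If all of the low level is on no statin, 0.8–5.0 of 10 points remain, with power 6–56% for two levels and 37–88% for three. If half is, 0.4–2.5 of 5 points remain, with power 5–18% and 12–32%.

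**A direct no-statin versus any-statin contrast.** With 75 no-statin patients, SE = √(1012.5/75 + 1012.5/675) = 3.87 and power for 10 points is 73%. With half that number (37.5), SE = √(1012.5/37.5 + 1012.5/712.5) = 5.33 and power is 47%, against 19% for the three-level test in the same case. That count equals the SAP's small-subgroup limit, 5% × 750 = 37.5.

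**The case against.** The strongest reply is that Phase 2 does not compare low with moderate intensity. It compares monotherapy with stable statin therapy, in an integrated analysis of six studies. The low level also holds daily low-dose and alternate-regimen users, who on that evidence belong with the 22% group. No-statin patients in this trial may take ezetimibe, fibrates or PCSK9 inhibitors, so they need not be on monotherapy. All of this stands. It is why three levels alone gain little if few low-level patients take no statin.

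The two-level split also has a rationale. Protocol 4.2.3 describes earlier experience mainly with low- and moderate-dose statins, so high intensity is the less-studied background. If the effect were 17 in high and 22 elsewhere (same 50/40/10 shares, SD 15), the two-level test would have 58% power and the three-level test 47%. Neither grouping is always better, which is a reason to keep both.

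On safety, the 1.4- to 2-fold rise in statin exposure in Protocol 4.2.3 concerns high-dose statins. Atorvastatin 80 mg and rosuvastatin 40 mg are already in the high level, so the existing split captures much of that question.

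A reader might infer that the addendum's LDL-C table, "Efficacy Subgroup Analysis: Percent Change from Baseline to Week 12 in Low Density Lipoprotein Cholesterol (LDL-C) by Derived Baseline Statin Intensity", was needed because of the merger. The addendum cites only issues of clinical interest and does not state the table's levels. Elsewhere (17.2.3.1) the SAP uses derived factors to correct mis-stratification. The documents do not support that inference.

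**Conclusion.** The point holds as a minor one. The merger is unexplained, unnecessary given the small-subgroup rule, and out of step with how patients are randomized and modelled. What is missing is a pre-specified adjusted treatment difference, confidence interval and interaction test for the low level.

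Three stronger readings might be drawn, and the documents do not support them:
- That the merger removes the expected difference. It dilutes it: 8–50% is kept across the assumed shares.
- That the plan provides nothing for the low level. By-arm descriptive statistics are planned, and an unadjusted difference can be worked out from them.
- That three levels would reliably reveal the difference. The gain from 14% to 63% power needs every low-level patient to be on no statin; with half it is about 7% to 19%.

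The level shares and the no-statin share are not in the documents, so no single power figure should be quoted without them. The subgroup analysis lies outside the testing hierarchy, and the primary analysis is unaffected.

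**What to change.** In SAP 17.2.4:
- Report the three randomized levels (low; moderate; high) with a 2-df interaction test, merging only under the existing 5% rule.
- Add a pre-specified no-statin versus any-statin contrast where numbers allow, since this is the contrast that the Phase 2 figures concern.
- Keep low-or-moderate versus high as an additional row.

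Use the same levels in the adverse-event subgroup tables under SAP 18.1.1.

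The cost is SAP wording and a few more exploratory rows; no new data are needed. The low-level interval will be wide: half-width 7.2 points with 75 patients, and 10.2 points (1.96 × √(1012.5/37.5)) at the 5% limit.
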